## Secondary efficacy endpoints:

- Absolute values and changes of blood hemoglobin level (g/L) after 4, 8 and 12-weeks of treatment in the study groups.
- Changes in average values of iron metabolism parameters (ferritin, transferrin, percent transferrin saturation, serum iron) after 4, 8 and 12 weeks of iron-deficiency anaemia treatment, as compared with the baseline value in the study groups.
- The frequency of response to therapy, determined as an increase in haemoglobin level by 20 g/L and more after 12-weeks of iron-deficiency anemia treatment in the study groups.
- Frequency and severity of all adverse events observed during the study therapy in the study groups.

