#### 9.1.3 Analysis of the secondary effecacy endpoints

#### Secondary efficacy endpoints:

All secondary efficacy analysis will be considered explorative, therefore, no multiplicity correction will be done for any tests, and no formal power calculation will be provided for the test results.

• Absolute values and changes (compared to baseline) of blood hemoglobin level (g/L) after 12 weeks of treatment (during the final visit) between the study groups.

Values at individual time points and values of change between the individual time points will be compared using the t-test or Mann-Whitney test depending on the normality of the distribution (which will be tested using Shapiro-Wilk test).

Additionally, it is planned to use ANCOVA for analysis of changes in the assessed parameters over time where group will be a fixed factor, screening hemoglobin level will be a covariate, and hemoglobin level at Week 12 will be a response variable.

• Changes in average values of iron metabolism parameters (ferritin, transferrin, percent transferrin saturation, serum iron) during the treatment period (from screening till the final visit) in the study groups.

Values at individual time points (baseline and Week 12) and values of change between the individual time points (baseline and Week 12) will be compared using the t-test or Mann-Whitney test depending on the normality of the distribution (which will be tested using Shapiro-Wilk test).

• The percentage (%) of subjects with response to the therapy, determined as an increase in hemoglobin level by 20 g/L and more after 12-weeks of treatment (from screening till the final visit) in the study groups.

Comparison between the two groups will be performed using the Fisher's exact test or chi-square test depending on the number of expected observations per cell (<5 or  $\geq$ 5). Two-sided 95% confidence interval will be calculated using exact Clopper-Pearson method.

These changes will be compared between the groups using the t-test or Mann-Whitney test depending on the normality of the distribution (which will be tested using Shapiro-Wilk test).

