3.2. Processing missing data

A method of filling in the missing data based on maximum likelihood estimation (MLE) for the primary endpoint will be applied if needed.

The analysis of the rest of endpoint types and other parameters will be performed only on the basis of the available information without filling in the missing data in view of the short duration of the clinical study.

4. Study participants

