8.2. Analysis of the secondary endpoint

- Absolute values and changes in hemoglobin level (g/L) after 4, 8, and 12 weeks of therapy (determined at the final visit) between the study groups.
- Changes in iron metabolism parameters mean values (ferritin, transferrin, percent transferrin saturation, serum iron) during the therapy period (from the screening to the study end visit) in the study groups.
- The responder rate (%) was determined as an increase in the hemoglobin level by ≥ 20 g/L after 12 weeks of treatment (from screening to the study end visit) in the study groups.

The data will be checked for compliance with the normal distribution law using the Shapiro-Wilk test.

Intergroup comparison of secondary endpoints related to quantitative scales will be performed using Student's t-test for independent samples if the data correspond to the normal distribution law; otherwise, the Mann–Whitney U test will be applied to independent samples.

Intergroup comparisons of secondary endpoints related to categorical scales will be performed using Pearson's chi-square test if the number of points in each cell of the crosstab is ≥ 5 , or Fisher's exact test if at least one of the crosstab cells contains < 5 points.

The dynamics will be assessed using ANOVA methods with repeated measurements if the data correspond to the normal distribution; otherwise, the Friedman test will be applied.

9. Safety analysis

Safety evaluation of the study therapy will be performed throughout the study and will be based on the detection of any adverse events occurring during the study. The following will be performed:

- Physical examination, including measurement of blood pressure and heart rate, and gastrointestinal disorders identification (at the screening, during the second visit, and the final visit).
- Complete blood count (at screening and in 4, 8, and 12 weeks of treatment);
- Blood biochemistry (at screening and after 12 weeks of treatment);
- Clinical urinalysis, pregnancy test (at screening and in 12 weeks);
- Registration of concomitant therapy (at each visit).

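### SAP 8.2 tests change over time with methods that give no arm-by-visit comparison under Friedman and use only patients with every visit; one mixed model would supply it

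*SAP*

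**What the plan says.** Protocol 4.1 lists as a secondary endpoint "Absolute values and changes of blood hemoglobin level (g/L) after 4, 8 and 12-weeks of treatment in the study groups", with a matching item for ferritin, transferrin, transferrin saturation and serum iron. SAP 8.2 repeats the haemoglobin item ("Absolute values and changes in hemoglobin level (g/L) after 4, 8, and 12 weeks of therapy") and adds that it is between the study groups.

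SAP 8.2 then gives two layers of analysis for quantitative parameters:

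- Intergroup comparison: "t-test for independent samples if the data correspond to the normal distribution law; otherwise, the Mann–Whitney U test will be applied to independent samples".
- Change over time, in a separate sentence: "The dynamics will be assessed using ANOVA methods with repeated measurements if the data correspond to the normal distribution; otherwise, the Friedman test". The sentence names no arm factor, no arm-by-visit term and no rule for a patient with a missed visit.

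SAP 3.2 says that endpoints other than the primary are analysed "only on the basis of the available information without filling in the missing data".

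Protocol 9.1.3 has one further model: "Additionally, it is planned to use ANCOVA for analysis of changes in the assessed parameters over time where group will be a fixed factor". Its covariate is screening haemoglobin and its response is Week 12 haemoglobin only. The same section states: "All secondary efficacy analysis will be considered explorative".

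**The concern.** The trial compares two products, and haemoglobin is expected to rise in both arms. A test that shows only that values change over visits says nothing about the products. Friedman ranks the visits within each patient, so it can neither estimate nor test a treatment effect or a treatment-by-visit effect. The normality check sends skewed parameters, of which ferritin is a likely example, down that branch. Whether a joint comparison of the arms over visits is possible at all then depends on the outcome of a Shapiro-Wilk test.

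Both methods in their standard form also need a full row per patient. With no fill-in, a patient who misses Week 4 or Week 8, or leaves before Week 12, drops out of this analysis. The remaining set is selected after randomisation. SAP 4.3.2 admits a patient to the ITT set on one efficacy visit, so the analysis set includes patients whom these methods cannot use.

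**Working it through.** **1. The plan's own figures.** Inputs from SAP 2.3: 143 per arm, 286 completers, 15% premature discontinuation, 336 randomised. 286 / (1 - 0.15) = 336.5, which agrees with 336 to within rounding. In reverse, 336 x 0.85 = 285.6, or about 286. The synopsis (Number of subjects) gives 15% as the most that will drop out, so 286 is the count at the planned maximum.

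**2. Patients with all four measurements.** The documents give no rate of missed interim visits. Assume that a fraction m of completers misses each of Weeks 4 and 8 independently: complete rows = 336 x 0.85 x (1 - m)^2.

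| m (assumed) | calculation | complete rows |
|---|---|---|
| 0% | 285.6 | 286 |
| 2% | 285.6 x 0.9604 | 274 |
| 5% | 285.6 x 0.9025 | 258 |
| 10% | 285.6 x 0.81 | 231 |

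As a check on the need for complete rows, one cell was set to missing in a 20-patient, four-visit data set. A standard Friedman routine returned no result, and a standard repeated-measures ANOVA routine rejected the data as unbalanced.

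**3. What Friedman detects.** Simulation with 143 per arm, four visits and 1,000 runs. Assumptions: reference-arm mean rise of 0, 5, 9 and 12 g/L; test-arm rise scaled down to give the stated Week 12 difference; between-patient and within-patient SD 8 g/L each. Share of runs with p < 0.05:

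| Week 12 arm difference | Friedman (arms pooled) | Repeated-measures ANOVA, arm by time | Mann-Whitney, Week 12 change |
|---|---|---|---|
| 0 g/L | 100% | 6.1% | 6.5% |
| 3 g/L | 100% | 48.9% | 58.4% |
| 5 g/L | 100% | 93.3% | 94.6% |

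Friedman run within the test arm alone also rejected in 100% of runs in each row. It responds to the rise over time and not to the arm difference. The assumed SDs imply an SD of change of sqrt(2) x 8 = 11.3 g/L, below the plan's 15 g/L, so the last two columns illustrate the contrast and are not power figures for this trial.

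**4. How likely the Friedman branch is.** For lognormal data with n = 143 and assumed sigma 0.3, 0.5 and 0.8 (300 runs each), Shapiro-Wilk rejected normality in 96%, 100% and 100% of runs.

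**5. Whether another section supplies the comparison.**

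- Appendix 1, secondary-endpoint Tables 3-12, have a group-comparison row with a p-value for absolute values at screening and Weeks 4, 8 and 12, and for change from screening at Weeks 4, 8 and 12. They cover haemoglobin and all four iron parameters. These are separate tests per visit, with no adjustment for baseline or strata.
- Appendix 1, Table 2 (analysis of variance) has an intercept, screening haemoglobin and group. It has no visit and no interaction term.
- No shell holds a repeated-measures ANOVA or Friedman result.

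So each visit has a between-arm test, and nothing joins the visits into one adjusted comparison.

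**The case against.** The strongest reply is that the arms are already compared at every visit. SAP 8.2 prescribes between-arm tests, by rank if the data are not normal, and Tables 3-12 carry them for every marker on all available data. That stands. A reader might infer from the Friedman sentence that skewed parameters get no comparison between arms over the course of treatment. The documents do not support this, because ferritin gets a Mann-Whitney test at Weeks 4, 8 and 12 whatever happens in the longitudinal test.

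The second reply is that the sentence on dynamics may be meant within each arm. SAP 8.2 uses the term intergroup for the other tests and not for this one, and no listed endpoint is an arm-by-visit interaction. Friedman is a proper test for a within-arm question. This reading is possible. The SAP does not say which is meant, and on this reading the longitudinal test does not contribute to the comparison between products.

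The third reply concerns size. A reader might infer that at least 50 patients are lost (336 - 286 = 50). That treats 15% as a floor, whereas the synopsis gives it as a ceiling, so dropout alone removes up to about 50. Nor do the secondary comparisons as a whole rest on completers, because the per-visit tests need no complete rows. Row deletion itself is implied by the standard methods and is not stated in the SAP, whose wording on repeated-measures ANOVA is loose.

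Last, the stakes are low. Protocol 9.1.3 makes these analyses exploratory, and the Week 12 haemoglobin comparison has its own ANCOVA, both as the primary endpoint and in Protocol 9.1.3.

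**Conclusion.** The point holds as a low-severity improvement. The longitudinal method in SAP 8.2 cannot compare the arms when the Friedman branch is taken, names no arm term when the ANOVA branch is taken, and in standard form uses complete rows only: about 286 of 336 patients at the planned maximum dropout, or 258-274 if 2-5% also miss each interim visit. The missed-visit rates are assumptions. The gap is confined to an adjusted arm-by-visit comparison that uses partial data. The per-visit between-arm tests remain, and the primary non-inferiority conclusion does not depend on any of this.

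**What to change.** Replace the sentence on dynamics in SAP 8.2 with one mixed model for repeated measures per quantitative parameter:

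- Response: change from screening at Weeks 4, 8 and 12, with ferritin on the log scale.
- Terms: treatment, visit, treatment by visit, baseline value, sex and haemoglobin stratum (80-94 vs 95-110 g/L).
- Covariance: unstructured across visits.
- Report: between-arm difference with 95% CI at each visit, in a new table shell.

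The model uses every patient with a baseline and at least one later value, and it needs no fill-in, so it is consistent with SAP 3.2. The per-visit t or Mann-Whitney tests may stay as supportive. If a within-arm description of change is also wanted, the SAP should label it as such.

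Cost: SAP wording, one shell and slightly more analysis work, with no new data. The trade-off is a distributional and covariance assumption, and reliance on data missing at random, in place of a rank test. Protocol 9.7 already provides for recording such a change with its justification.

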9.1. Adverse events

The safety assessment will include determining the total number, frequency, and severity of:

- 1. Adverse events (AEs), regardless of their relation to the treatment;
- 2. AEs associated or potentially associated with the medicinal product;
- 3. AEs requiring treatment discontinuation.

Adverse events will be coded using the MedDRA nomenclature in the latest version. These will be represented by the preferred term (PT) and systemic organ class (SOC).

Methods of descriptive statistics will be used to represent the results. Comparison of the incidence of new cases of AE in the study groups will be carried out using Fisher's exact test or Pearson's χ^2 test, depending on the number of observations in one cell (< 5 or \geq 5).

Changes in the results of laboratory tests over time and the incidence of abnormal test results (based on the reference values of the central laboratory) will be summarized by groups, and a comparison will be made between the groups using appropriate tests for quantitative and qualitative data.

Safety data will be analyzed using the methods designated for the application of efficacy data evaluation.

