#### Safety Measurements

Safety evaluation will include:

1) Determination of the total number, frequency and severity of:

- I. adverse events (AEs) irrespective of their relation to treatment;
- II. AEs related or possibly related to the treatment received;
- III. AEs requiring termination of the therapy.

2) Complaints on digestive system disorders (defined through MedDRA SMQ for the corresponding symptoms), considered as related to the study therapy by the investigator, will be analyzed separately.

Descriptive statistics will be used for presentation of the result. Comparison of all AE incidence between the study groups will be performed using the Fisher's exact test or chi-square test depending on the number of expected observations per cell (<5 or  $\geq 5$ ), and comparison of intensity (and possible causal relationship between the treatment received and the AE) will be performed using Cochrane-Armitage trend test for the ordered categorical data.

3) Changes in laboratory test results (assessed in central laboratory) over time and frequency of abnormal test results (according to the normal ranges of central laboratory) will be summarized by group and also compared by group using corresponding tests for quantitative data and qualitative data (see below).

4) Changes in vital signs over time and frequency of abnormal physical examination findings will be summarized by group and also compared by group using corresponding tests for quantitative data and qualitative data (see below).

Quantitative data will be compared using the t-test or Mann-Whitney test depending on the normality of the distribution (which will be tested using Shapiro-Wilk test).

Qualitative data will be compared using the Fisher's exact test or chi-square test depending on the number of expected observations per cell (<5 or  $\geq 5$ ).

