## 9 Statistical methods description

## 9.1 Analysis methods description

Statistical analysis will be performed using R Project specialized software.

All continuous (quantitative) indicators will be submitted in the form of the following descriptive statistics parameters:

- Number of observations,
- arithmetic mean,
- 95 % confidence interval (CI) for the average,
- standard deviation,
- median,
- interquartile range,
- minimum,
- maximum.

All the ordinal, categorical and qualitative indicators will be submitted in the form of the following descriptive statistics parameters:

- absolute frequency (observations number),
- relative frequency (expressed as percent),
- 95% CI for proportion.

All the performed types of statistical analysis will be identical in the study product Ferrum Lek® group and in the comparator MALTOFER® group.

The concomitant diseases and AEs will be coded using MedDRA terms.

This section contains a brief description of the planned analysis. Full analysis will be presented in the statistical analysis plan.

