#### 9.1.4 Safety parameteres analysis

Safety evaluation will include:

- 1) determination of the total number, incidence and severity of the folowing:
  - I. adverse events (AEs), regardless of their relationship to the treatment;
  - II. AEs associated or potentially associated with the drug;
  - III. AEs leading to discontinuation.

2) Gastrointestinal disorders (determined by means of a standardized MedDRA query for the corresponding symptoms), regarded by the Investigator as related to the study therapy, will be analyzed separately.

Methods of descriptive statistics will be used to represent the results. A comparison of the incidence of new AE cases in the study groups will be performed using the Fisher's exact test or

the chi-square test, depending on the number of proposed observations in one cell (<5 or  $\ge 5$ ), and a comparison of the severity (and the possible causality between the study drug and AE) will be conducted using the Cochran—Armitage test for linear trends for ordered categorical data.

3) Changes in the results of laboratory studies (conducted in the central laboratory) over time and the incidence of abnormal results of studies (based on the reference values of the central laboratory) will be summarized by group, and a comparison will be made between the groups using appropriate tests for quantitative and qualitative data (see below).

4) Changes in the vital signs over time and the incidence of pathological abnormalities revealed during physical examination will be summarized by group, and a comparison will be made between the groups using appropriate tests for quantitative and qualitative data (see below).

Comparison of quantitative data will be conducted using the t-test or the Mann—Whitney test, depending on the distribution normality (which will be estimated using the Shapiro—Wilk test).

Qualitative data will be compared using the exact Fisher's exact test or the chi-square test, depending on the number of proposed observations in one cell (<5 or  $\geq 5$ ).

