ITP	Iron transport proteins 1 and 2
RE	Reticuloendothelial (cells)
RES	Reticuloendothelial system
SBP	Systolic blood pressure
SAE	Serious adverse event
SOD	Superoxide dismutase
SOP	Standard operating procedure
TF	Transferrin
TfR	Transferrin receptor
FL	Federal law
Full name	First name, Patronymic, Last name
CNS	Central nervous system
Ср	Ceruloplasmin
RR	Respiration rate
HR	Heart rate
ECG	Electrocardiography

1. Introduction

This study is planned and carried out to demonstrate the non-inferiority and safety of Ferrum Lek[®] (iron (III) hydroxide polymaltosate), 100 mg chewable tablets (Lek d.d., Slovenia), compared to MALTOFER[®] (Vifor S.A., Switzerland), in subjects with mild and moderate iron deficiency anemia.

The objective of this Statistical Analysis Plan is more detailed, compared to Section 9 of the study protocol, description of the main principles of the protocol-based statistical analysis, description of the primary and secondary endpoints analysis methods as well as other data obtained during the study.

This Plan stipulates for conformance of the scheduled and conducted statistical analysis to the study protocol, including the definition of the analysis data sets, transformations and calculations for the endpoints, observations quantity needed, etc.

2. Study objectives and design

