9.2. Other safety endpoints

No other safety endpoints are foreseen in this study.

10. Exploratory analysis

In the course of this study, exploratory analysis is not envisaged.

11. Interim analysis

One interim analysis is planned to assess the primary and secondary efficacy endpoints when a group of patients with available data on the primary endpoint will include at least 200 subjects [100 patients in each treatment group: in the main treatment group of patients taking Ferrum Lek[®] (iron (III) hydroxide polymaltosate complex) and in the control group of patients taking MALTOFER[®] (iron (III) hydroxide polymaltosate complex]. Safety and efficacy will be assessed in all patients who have received at least one dose of randomized therapy at the time of the interim analysis. Based on the results of the interim analysis of the primary and secondary statistical endpoints of efficacy and safety, the Sponsor may decide to discontinue the study if the endpoints of the study are achieved in accordance with the protocol based on the results of the interim analyses or the sample size can be recalculated using the results of the interim analysis.

STATISTICAL ANALYSIS PLAN

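### The SAP does not carry over the protocol's separate analysis of treatment-related gastrointestinal disorders, and its AE table layouts give shares of events rather than of patients

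*SAP*

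**What the plan says.** **Protocol.** Section 9.1.4 item 2 says that gastrointestinal disorders identified by a standardised MedDRA query and "regarded by the Investigator as related to the study therapy, will be analyzed separately". Section 4.1 (Safety Measurements) and the synopsis repeat the plan; the wording in 4.1 begins "Complaints on digestive system disorders (defined through MedDRA SMQ for the corresponding symptoms". None of the three places names the query. Section 9.1 leaves the detail to the SAP: "Full analysis will be presented in the statistical analysis plan". The same section asks for absolute frequency, relative frequency and a 95% CI for every categorical indicator.

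**SAP.** Section 1 declares agreement with the protocol: "This Plan stipulates for conformance of the scheduled and conducted statistical analysis to the study protocol". Section 9 keeps the data collection, namely "gastrointestinal disorders identification (at the screening, during the second visit, and the final visit". Section 9.1 then opens with "The safety assessment will include determining the total number, frequency, and severity of" and lists three categories: all AEs, AEs related or possibly related to the product, and AEs requiring discontinuation. On grouping it says only "These will be represented by the preferred term (PT) and systemic organ class (SOC". It also plans to compare the incidence of new AE cases between groups. Section 9.2 closes with "No other safety endpoints are foreseen in this study".

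**SAP Appendix 1, adverse events.** Table 1 has rows for all AEs, SOC and PT. Its columns are a count, the share of all AEs, the share of AEs within the product, and a Fisher p-value. Tables N break the same rows down by relatedness, action taken and seriousness, again as counts and shares of AEs.

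**The concern.** Comparative safety is the stated secondary objective (Protocol 3.2). In the product information reproduced in Protocol 2.1.1 and 2.1.2, every reaction classed as very common or common for either product is gastrointestinal. Item 2 is the one protocol analysis aimed at that harm. An analyst who followed the SAP and its layouts as written would not produce it.

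The only combined gastrointestinal summary left in the layouts is the SOC row. Both labels put faeces discolouration under gastrointestinal disorders at 23% of patients, and Protocol 2.1.1 and 2.3.8 call it clinically insignificant. The SOC row would therefore mix a harmless colour change with nausea, diarrhoea, vomiting, constipation and abdominal pain. A share of AEs also depends on how many other AEs an arm reports, so it cannot be read as a rate of affected patients. Because the trial is open-label and the query is unnamed, the choice of terms and the treatment of discolouration could be settled after the data have been seen.

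**Working it through.** **1. Text comparison.**

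| Protocol 9.1.4 | SAP 9.1 | AE layouts |
|---|---|---|
| Item 1: all, related and discontinuation AEs | carried over | rows by SOC and PT; relatedness and withdrawal in Tables N |
| Item 2: related gastrointestinal disorders by MedDRA query | not mentioned | no row or table |
| Relative frequency with CI (Protocol 9.1) | incidence comparison mentioned | shares of AEs only; no patient denominator or CI |

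**2. Can the planned rows stand in for item 2?** PT rows isolate discolouration, and Tables N isolate related events. One patient can appear under several PTs, so these rows cannot be added up to patients with at least one other gastrointestinal AE.

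**3. Plan figures.** The plan gives no rate, precision or power for gastrointestinal AEs, so there is no figure of its own to reproduce on this point. Its sample size concerns haemoglobin only. From it I take 168 randomised per arm. The label rate of 23% gives 0.23 × 168 = 38.6, about 39 patients per arm with discolouration.

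**4. Event shares against patients (assumed counts, one event per affected patient).** If one arm has 20 gastrointestinal events among 60 AEs and the other 10 among 30, both shares are 33%. The patients affected are 20/168 = 11.9% and 10/168 = 6.0%.

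Now take intolerance in 17 vs 34 patients, 39 discolouration events per arm and 34 other AEs per arm:
- without discolouration: 17/51 = 33% vs 34/68 = 50%;
- with discolouration: 56/90 = 62% vs 73/107 = 68%;
- with 17 or 50 other AEs per arm instead of 34, the pooled pair is 77% vs 81% or 53% vs 59%.

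Counted as patients, 17/168 vs 34/168 is about 10% vs 20%. The 95% CI for that difference is 0.10 ± 1.96 × √(0.09/168 + 0.16/168) = 0.024 to 0.176.

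**5. Effect of pooling on a patient-level comparison.** Intolerance rates are assumed; discolouration is equal in both arms. The pooled rate is 1 − (1 − p)(1 − d) if the two are independent and p + d if they never coincide, where p is the intolerance rate and d the discolouration rate. Power is for a two-sided 5% chi-square test, n = 168 per arm, normal approximation with pooled null variance. For intolerance of 10% vs 20%:

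| Discolouration recorded | Independent | No overlap |
|---|---|---|
| none | 0.73 | 0.73 |
| 2% | 0.67 | 0.69 |
| 5% | 0.60 | 0.63 |
| 10% | 0.49 | 0.56 |
| 23% | 0.32 | 0.47 |

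At 23% the pooled rates are 30.7% vs 38.4% (independent) or 33% vs 43% (no overlap). Other assumed contrasts, no discolouration against 23% independent: 5% vs 15%, 0.87 to 0.33; 10% vs 25%, 0.96 to 0.60 (0.80 with no overlap); 5% vs 10%, 0.41 to 0.12.

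**The case against.** **Omission is not withdrawal.** A reader might infer that the SAP has cancelled the gastrointestinal analysis. The documents do not support that. Item 2 stands in three protocol places, the SAP says it conforms to the protocol, and Protocol 9.7 requires deviations from the statistical plan to be described and justified; the SAP declares none here. The analysis is still owed. What stands of the concern is that the SAP gives it no method and no table.

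**Patient-level incidence is not wholly absent.** SAP 9.1 speaks of comparing AE incidence, which can be read as patients, and Protocol 9.1 asks for relative frequencies with CIs. The layouts do not override that text. They are nonetheless what a programmer will follow, and none of them has a patient denominator.

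**Pooling is a separate matter from the omission.** The query is unnamed, so item 2 carried over word for word might itself include discolouration. The power figures therefore measure the SOC row as a substitute; they do not measure the loss of item 2. Excluding discolouration and adding a CI for the difference are additions to the protocol's wording.

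**The rates are assumed.** Both products contain the same complex at the same dose, and their labels list the same gastrointestinal terms in the same frequency classes. Protocol 2.3.6.1 cites a study in which stool colour change was among effects with 10% incidence, so 23% may be too high. All of this stands, and it limits the size of the point without closing the gap.

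**Conclusion.** The point holds as a secondary gap that should be closed. A protocol analysis serving the secondary safety objective has no method or table in the SAP, and the AE layouts report event shares that can hide a difference in patients affected.

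The size is modest. No decision rule depends on the result, and the primary conclusion cannot change. PT rows and Tables N will still show discolouration and relatedness by event. It would go too far to say that the plan will mask a tolerability difference: the documents give no reason to expect one, and a five-point gap would mostly be missed even without pooling (0.41 for 5% vs 10%). The fall from 0.73 to between 0.32 and 0.47 applies only to assumed intolerance of 10% vs 20%, discolouration in 23% of both arms, and a reader who relies on a pooled gastrointestinal row counted in patients. The range runs from independence to no overlap, and the loss shrinks as recorded discolouration falls.

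**What to change.** - Add item 2 to SAP 9.1 and to the AE tables: number and percentage of safety-population patients per arm with at least one treatment-related gastrointestinal AE, with a 95% CI for the difference between arms.
- Name the MedDRA query before database lock.
- Show faeces discolouration on its own line, with the same patient denominator, and exclude it from the combined row.
- Add patient n and % to the existing SOC and PT rows, keeping the event counts.

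The cost is a short SAP revision and one or two extra safety rows. AEs are already to be MedDRA-coded and relatedness is recorded for each one, so no new data, visits or staff are needed.
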